5.0 SUBJECT REIMBURSEMENT

Subjects may be reimbursed for their time and travel and any expenses associated with each study visit, as allowed by study site policies. Subjects will not be reimbursed for those scheduled study visits that they do not attend.

6.0 STUDY WITHDRAWAL

Subjects may be terminated or withdrawn from the study for the following reasons:

- Voluntary withdrawal – the subject voluntarily chooses not to further participate in the study
- *Lost to follow-up – the subject is more than one month late (beyond the late visit window) to a study visit and 3 documented attempts to contact the subject are unsuccessful. A subject who misses a study visit but attends a subsequent visit will no longer be considered lost to follow-up.
- *In the physician's opinion, it is not in the best interest of the subject to continue study participation.
- Subject death.

**Where possible, subjects will be followed for safety to study completion. Safety follow-up will include a review of adverse events (AEs). A safety follow-up assessment may be performed either via a phone or email contact or a physician visit.*

Any study subject who does not attend the scheduled follow-up visit should be contacted by site personnel to determine the reason for the missed appointment. The reason for the missed visit should be determined and documented in the subject's study records. All subjects enrolled

(including those withdrawn or lost to follow-up) shall be accounted for with appropriate documentation.

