2.1 Primary outcome variables

The primary symptom outcome variables include self-reported Nasal Obstruction Symptoms Evaluation (NOSE) score and VAS of nasal obstruction.

The primary independent objective variables include several categories: 1) variables that index general disease severity (Computerized Tomography (CT) staging and endoscopic examination score), 2) peak inspiratory flow measurements of nasal physical resistance.

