4.0 PROCEDURES

4.1 Research Design

The study will be conducted by the Department of Otolaryngology, The Ohio State University School of Medicine, in conjunction with Aerin Medical. This study is a prospective, case series design, involving a group of patients with chronic nasal obstruction symptoms. The study is a longitudinal design, involving two test sessions: one at baseline (pre-treatment) and one at 90 days post-treatment.

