4.2 Study Size

Up to Twenty (20) patients meeting the inclusion/exclusion criteria will be recruited.

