4.9 Data Analysis

Treatment effectiveness

Outcome variables: patient's ratings of nasal obstruction via a VAS and NOSE score as well as the SNOT-22 questionnaire and peak inspiratory flow rate. One-way ANOVA with repeated measures will be used to compare post-treatment vs. baseline measurements and determine the effectiveness of the treatment.

Hypothesis:

Nasal valve region airflow and airflow induced cooling is critical for patients' subjective nasal patency.

Many publications suggest that sensory feedback is as important to perception of nasal obstruction as nasal resistance. For example: Topical or oral application of menthol produces the illusion of decongestion and improved nasal airflow without actually altering nasal resistance¹⁰. Topical application of local anesthetics results in an artificial sensation of nasal obstruction, presumably due to blocking of the trigeminal afferents¹¹.

The Ohio State University (OSU) staff have published a series of studies^{6,12,13} with individualized Computational Fluid Dynamics models and demonstrated that nasal cooling during breathing at the nasal valve region and the nasal trigeminal nerve sensitivity are key to the perception or absence of nasal obstruction. The combination of these variables can predict the subject's ratings (excellent, normal and moderately obstructed) with 89.3% success. It is likely that nasal valve width and shape may have an optimal range in order to achieve both low nasal resistance and high regional mucosal cooling (see Fig. 5). This study will examine a broad list of factors that may contribute to patients' subjective outcomes, not just limited to nasal resistance alone, that include CFD simulation of nasal airflow, mucosa cooling and mucosa sensitivity responding to that cooling.

[figure not shown]

Figure 5. Computational simulation of nasal cooling

- a) high regional cooling, no complaints
- b) low nasal cooling with moderate ratings of nasal obstruction

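### Section 6.0 makes no provision to collect NOSE and VAS from treated subjects who withdraw or miss day 90, so they drop out of the only effectiveness comparison

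*Combined protocol and SAP*

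**What the plan says.** - **Outcomes.** Section 2.1: "The primary symptom outcome variables include self-reported Nasal Obstruction Symptoms Evaluation (NOSE) score and VAS of nasal obstruction".
- **Timing.** Section 4.1 describes a design "involving two test sessions: one at baseline (pre-treatment) and one at 90 days post-treatment". Table 1 (section 4.7) shows day 90 as the only post-treatment NOSE and VAS assessment, and it is also study exit.
- **Size.** Section 4.2: "Up to Twenty (20) patients meeting the inclusion/exclusion criteria will be recruited". No dropout allowance is given.
- **Analysis.** Section 4.9: "One-way ANOVA with repeated measures will be used to compare post-treatment vs. baseline measurements and determine the effectiveness of the treatment". No analysis set, missing-data method or sensitivity analysis is stated.
- **Leavers.** Section 6.0 lists four exit routes. Two carry an asterisk: loss to follow-up and the physician's decision. For these, "Safety follow-up will include a review of adverse events (AEs"), and "A safety follow-up assessment may be performed either via a phone or email contact or a physician visit". The first route, "Voluntary withdrawal – the subject voluntarily chooses not to further participate in the study", has no asterisk.
- **Non-attenders.** Section 6.0 has site staff contact anyone who misses the follow-up visit, to find out and document why. A subject counts as lost only when more than a month past the late window and after three failed contact attempts.

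**The concern.** NOSE and VAS are filled in by the subject and need no examiner or scanner. The day-90 visit, by contrast, is expected to take 2 to 3 hours (section 4.6) and may include a research CT. Some subjects may decline that visit yet be willing to answer a short questionnaire, and the site will already be in touch with some of them. The plan uses those contacts for adverse events or for the reason for absence, and leaves the primary outcomes uncollected.

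At stake is the pre-post change in a single-arm study of at most 20 subjects. There is no control group and no interim post-treatment score to fall back on. Under section 4.7 a subject counts as enrolled on arrival for the procedure, so a subject missing at day 90 will nearly always have been treated.

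**Working it through.** The plan gives no dropout rate, effect size or power calculation, so there is no figure of its own to reproduce. The check has two parts.

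**1. What each route yields under the plan as written**

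| Route | Contact named in section 6.0 | Content named | NOSE/VAS named? |
|---|---|---|---|
| Lost to follow-up | Safety follow-up where possible | AE review | No |
| Physician-decided withdrawal | Safety follow-up where possible | AE review | No |
| Voluntary withdrawal | No safety follow-up attached | None | No |
| Missed day-90 visit | Contact by site staff | Reason for absence | No |

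With two time points, a one-way repeated-measures ANOVA is equivalent to a paired t-test on the change score. A subject with no post-treatment value has no change score and leaves the analysis.

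**2. How far completers could differ from all treated subjects**

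Inputs: N = 20 (section 4.2, taken at its maximum). The number missing m = 1, 2 or 4 is an assumption. Let C be the completers' mean improvement and f × C the mean improvement of the missing subjects; f is also an assumption.

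Mean over all treated = [(N − m)C + m f C]/N

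Relative overstatement by completers = N/[N − m(1 − f)] − 1

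| m | f = 0 (zero change) | f = 0.5 (half the improvement) |
|---|---|---|
| 1 | 20/19 − 1 = 5.3% | 20/19.5 − 1 = 2.6% |
| 2 | 20/18 − 1 = 11.1% | 20/19 − 1 = 5.3% |
| 4 | 20/16 − 1 = 25.0% | 20/18 − 1 = 11.1% |

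If f = 1 there is no bias. If f is above 1, because the absentees did better, completers understate the improvement.

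In NOSE points, the shift is (m/20) × the gap between completers' mean change and that of the missing. For assumed gaps of 10, 20 and 40 points:

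- m = 1: 0.5, 1 and 2 points
- m = 2: 1, 2 and 4 points
- m = 4: 2, 4 and 8 points

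**The case against.** **The text does not forbid collecting outcomes.** Section 6.0 says what safety follow-up includes, which is not a restriction to adverse events, and the contact may be a physician visit as well as phone or e-mail. This stands: the defect is absence of provision, not prohibition. But a site following the protocol has no instruction to take the scores, and the analysis has no rule for using them.

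**Missing the window does not by itself lose the outcome.** A subject is not lost until more than a month past the window, so a late visit is possible. This also stands, though the plan does not say whether late scores are analysed. Day 90 is study exit, so no later scheduled visit exists.

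**A reader might infer that the subjects lost are those who did badly, so the result is biased upward.** The documents do not support this. One exit route rests on the physician's judgement of the subject's interest, and section 8.1 lists scarring that obstructs the nose as a possible harm, so a link with poor outcome is plausible. But subjects who feel well may equally skip a long research visit.

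**Zero change is a severe assumption.** Entry requires NOSE of at least 60 (section 4.3), so regression to the mean alone would make some improvement likely. This stands. With 1 or 2 missing and a gap of 10 to 20 points, the shift is only 0.5 to 2 NOSE points.

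**The remedy has limits.** Subjects lost after three failed contacts are mostly beyond reach. Those helped are mainly physician-decided withdrawals, reachable non-attenders and voluntary leavers who still agree to contact. VAS is marked on a line for both nostrils and then each side (section 4.6), so it does not transfer to the phone. Remote values also mix mode and timing. These points shape the fix below but do not remove the gap.

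**Conclusion.** The point holds as a gap in data collection. No route out of the study, and no contact after a missed visit, provides for NOSE or VAS, and the paired analysis drops anyone without a post-treatment score. If non-attendance is related to outcome, the completers' change is biased; the direction cannot be known in advance.

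Under the assumption of zero change in the missing, the overstatement is 5%, 11% or 25% for 1, 2 or 4 of 20 missing, and about half that or less if they gained half as much as completers. The number missing is assumed throughout. A dropout rate should not be read from the feasibility percentages in Table 2, which count nostrils in another study. No claim is made about precision, since the plan sets no precision target.

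The change is worth making because it adds data the trial would otherwise not have, at small cost.

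**What to change.** 1. **Section 6.0, collection.** Provide for NOSE and VAS from every treated subject who withdraws or misses day 90 and still agrees to contact. Collect them at early exit, or at the missed-visit or safety contact, as close to day 90 as possible. Use a visit, e-mail or post for both scales, and phone for NOSE only. State that this also applies to voluntary withdrawals who agree to it. Record mode and date.
2. **Section 4.9, primary comparison.** Include these values, then repeat the comparison with in-clinic values only, to show whether mode and timing matter.
3. **Section 4.9, sensitivity analysis.** Add one analysis in which treated subjects still missing are given zero change from baseline.

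The cost is a few minutes per contact and two further runs of a simple analysis. Some difference in mode and timing has to be accepted. Unreachable subjects stay missing, and peak flow and CT are not recovered.

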7.0 ADVERSE EVENTS

Adverse events (AEs) may occur during the treatment phase or during the follow-up phase. Adverse events occurring after the baseline assessment but before the treatment procedure will be documented in the subject's medical record but will not count as related to the investigational device or procedure.

Each adverse event will be recorded in the corresponding subject's CRF. The Investigator will make a judgement as to its relationship and level of relatedness to the study device and/or study procedure. In addition, the Investigator will identify the date of onset, severity and duration of the AE. All adverse events will be monitored until they are adequately resolved or explained. If a subject reaches the 90-day follow-up visit and is experiencing a new or ongoing adverse event, the study sponsor should be contacted to discuss the need and/or methods for continued surveillance of the event.

The Investigator must submit to the Sponsor a report of any Serious Adverse Event (SAE), Serious Adverse Device Effect (SADE) or Unanticipated Adverse Device Effect (UADE) within 24 hours of knowledge of the event.

Sponsor Contact: [name]
[contact]
[contact]
Email: [contact]

In addition, the Investigator will report adverse events to the reviewing IRB (*as applicable*) according to the local reporting requirements.

Bleeding at anesthetic injection site	Mild	5.3	No reports		No reports	
Bleeding at treatment site	Mild	3.4	No reports		No reports	
Nasal obstruction from tissue edema	Mild	45.8	Mild	5.4	No reports	
			Moderate	1.8		
Disruption of mucosal flow / crusting	Mild	1.7	Mild	10.7	No reports	
			Moderate	1.8		

8.2 Potential Benefit

Potential benefit, associated with the use of the Vivaer™ System, is to offer a safe, minimally invasive treatment method to improve nasal breathing. Improved nasal breathing may have a positive effect on quality of life and health.

8.3 Minimization of Anticipated Risks

Risks associated with the Vivaer™ System are minimized by design. In addition, risks will be minimized through the use of an Investigator with a high degree of experience in nasal surgical and minimally invasive procedures. The Investigator will receive sponsor-led training in proper use of the device, prior to study initiation and as warranted throughout the study. The sponsor will monitor the study for any trends that would indicate a safety issue.

8.4 Potential Risks to Patient Confidentiality

In all clinical studies, confidentiality of protected health information may be breached due to study-related activities beyond those of routine clinical care. This risk will be minimized by not collecting personally identifying information on Case Report Forms (CRFs) or other study-related documentation to be provided to the study sponsor.

9.0 QUALITY ASSURANCE AND SUPERVISION BY AUTHORITIES

This study will be conducted in accordance with elements of E6 Good Clinical Practice Consolidated Guidance, ICH, April 1996, abbreviated requirements of 21 CFR 812.2(b) for Non-significant Risk (NSR) device studies, the Declaration of Helsinki, the Belmont Report, and IRB requirements.

All documents and data shall be produced and maintained in such a way to assure control of documents and data to protect the patient's privacy as far as reasonably practicable. The Sponsor and representatives of the FDA or other regulatory authorities are permitted to inspect the study documents (e.g., study protocol, CRFs, and original study-relevant medical records/files) as needed. All attempts will be made to preserve patient confidentiality.

The clinical site is subject to audit by study sponsor personnel or designee for protocol adherence, accuracy of CRFs and compliance with applicable regulations. Any evident pattern of non-compliance with respect to these standards will be cause for corrective action.

The study protocol, data-recording procedures, data handling as well as study reports are subject to an independent clinical Quality Assurance audit by the study sponsor, its designee, or health authorities.

10.0 STUDY MANAGEMENT

This study will be conducted in accordance with elements of E6 Good Clinical Practice Consolidated Guidance, ICH, April 1996, Abbreviated Requirements of 21 CFR 812 for NSR device studies, the Declaration of Helsinki, the Belmont Report and any conditions imposed by the reviewing IRB **or** US FDA or other regulatory agency.

The study sponsor has the overall responsibility for the conduct of the study according to all applicable regulatory requirements. The study sponsor will have certain direct responsibilities and will delegate other responsibilities to the Principal Investigator. The study sponsor and Principal Investigator will ensure that the study is conducted according to all applicable regulations. All personnel to participate in the conduct of this clinical trial will be qualified by education and / or experience to perform their tasks.

The study sponsor, Investigator or any person acting for or on behalf of a sponsor or Investigator shall act in accordance the applicable standards, guidelines and regulations.

11.0 INVESTIGATIONAL DEVICE MANAGEMENT

The Vivaer™ System is investigational and is not approved for commercial use in the United States. The investigator shall maintain adequate records of the receipt and disposition of all investigational devices. When trial enrollment is complete, the investigator shall return any unused devices to the sponsor or their designee. The device will only be used as part of this clinical trial in eligible patients and will be used according to its intended use. A copy of the Instructions for Use (IFU) accompanies each study device.

12.0 REQUIRED DOCUMENTS FROM THE INVESTIGATOR (PRIOR TO STUDY START)

At a minimum, the following documents will be provided by the investigational site to the study sponsor:

- Signed Investigator Agreement
- Signed Clinical Investigational Plan (CIP) Signature Page
- IRB approval
- IRB approved Informed Consent Form (ICF)
- Investigator and Co-Investigator's current Curriculum Vitae
- Investigator and Co-Investigator's current Medical Licenses

A site may not begin study participation until all of the above listed documents have been provided to the study sponsor.

13.0 TRAINING

The Vivaer System is intended for use by experienced medical personnel. The Investigator will be provided training by the study sponsor in the use of the device to familiarize them with the use of the Vivaer System prior to their participation in the clinical study.

Each study center will undergo protocol initiation including but not limited to a review of the following:

- Procedures for obtaining Informed Consent
- Procedures for completing Informed Consent Form
- Device usage instructions
- Reporting requirements
- CRF completion and correction procedures
- Vivaer System overview
- Protection of patient confidentiality

14.0 ETHICAL CONSIDERATIONS

The rights, safety and well-being of clinical investigation subjects shall be protected consistent with the ethical principles outlined in the Declaration of Helsinki. This shall be understood, observed and applied at every step in this clinical investigation.

It is expected that all parties will share in the responsibility for ethical conduct in accordance with their respective roles in the investigation. The Sponsor and the Investigator shall avoid improper influence or inducement of the patient, study monitor, clinical investigator or other parties participating in or contributing to the clinical investigation.

15.0 PROTECTION OF PATIENT CONFIDENTIALITY

At all times throughout the clinical investigation, confidentiality will be observed by all parties involved. All data shall be secured against unauthorized access. Privacy and confidentiality of information about each patient shall be preserved in the reports and in any publication. Each patient participating in this study will be assigned a unique identifier. All CRFs will be tracked, evaluated, and stored using only this unique identifier.

The investigational site will maintain a confidential study patient list (paper or electronic) identifying all enrolled patients. This list will contain the assigned study patient's unique identifier and name. The Site Principal Investigator (PI) bears responsibility for keeping this list confidential. This list will not be provided to the study sponsor and is only to be used at the study center.

Monitors and auditors will have access to the study patient list and other personally identifying information of study patients to ensure that data reported in the CRF corresponds to the person who signed the ICF and the information contained in the original source documents. Such personal identifying information may include, but is not limited to the patient's name, address, date of birth, gender, race and medical record number.

NOTE: The patient's name, medical record number or address will NOT be recorded in the monitor's visit report or the database; demographic data that may be recorded includes age, race, and gender.

Any source documents copied for monitoring purposes by the Sponsor will have patient identifiable information redacted and be identified by using the assigned patient's unique identifier in an effort to protect patient confidentiality.

16.0 DATA COLLECTION

Study data will be collected using standardized Case Report Forms (CRFs). The CRFs are designed to accommodate the specific features of the trial design. Modification of CRFs will only be made if deemed necessary by the study sponsor.

17.0 SOURCE DATA VERIFICATION

At a minimum, source data verification will be performed on all primary endpoint, secondary endpoint and safety data for each patient enrolled in this study.

18.0 STUDY SUSPENSION OR EARLY TERMINATION

The study can be discontinued at the discretion of the Site PI or Sponsor for reasons including, but not limited to, the following:

- Occurrence of adverse events unknown to date in respect to their nature, severity, or duration, or the unexpected incidence of known adverse events
- Obtaining new scientific knowledge that shows that the study is no longer valid or necessary
- Insufficient recruitment of patients
- Unanticipated adverse device effect (UADE) presenting an unreasonable risk to patients (Sponsor may terminate the study immediately)
- Persistent non-compliance with the protocol
- Persistent non-compliance with IRB or regulatory requirements

If the study is discontinued or suspended prematurely, the Sponsor shall promptly inform the clinical investigator(s) / investigational centers of the termination or suspension and the reason(s) for this. The IRB shall also be informed promptly and provided with the reason(s) for the termination or suspension by the Sponsor or by the Site PI / investigational center. Regulatory authorities and the personal physicians of the patients may also need to be informed if deemed necessary.

19.0 SITE CLOSE-OUT

At the time of the site close-out visit, the site monitor or designee will collect all outstanding study documents, ensure that the Investigator's files are accurate and complete, review record retention requirements with the Investigator, make a final accounting of all study supplies, and ensure that all applicable requirements are met for the study. The observations and actions made at this visit will be documented in a final closeout report.

